**Clinical Study of the WoundCare360 SiteSeal Adjunctive
Compression Device Following Interventional Endovascular
Procedures – NCT03234894**

Study Protocol:

Document Date: October12, 2015

PROTOCOL

SiteSeal™ Adjunctive Compression Device

1. **STUDY TITLE:** Clinical Study of the Wound Care 360° SiteSeal™ Adjunctive Compression Device Following Interventional Endovascular Procedures
2. **PRINCIPAL INVESTIGATOR:**
[name]
University of Kansas Medical Center
[name]
[name]
3. **SPONSOR:**
Wound Care 360° Inc.
[name]
[name]
[name]
4. **CLINICAL FACILITY:** Cardiac Intervention Lab
University of Kansas Medical Center
5. **STUDY MONITOR** [name]
6. **PROTOCOL DATE**
October 12, 2015
7. **PROTOCOL NUMBER**
15-012
8. **Version**
1.2

9. Purpose

This Clinical Study is a pivotal study to evaluate the safety of the SiteSeal™ Adjunctive Compression Device across a broad array of patients undergoing interventional endovascular procedures.

10. Synopsis

The study design is a single arm with 90 patients. The primary endpoints measure the risk for common femoral nerve damage and common femoral artery laceration from the blind placement of a Z-stitch in the soft tissue above the femoral bundle.

The sample size is 90 patients. The project objective is to demonstrate the safety of the device.

11. TRIAL PHASE

Pivotal Clinical Trial

12. NAME OF DEVICE

SiteSeal™

13. INTENDED USE

SiteSeal™ is intended for use in the compression of the femoral artery after cannulation. The device is intended for professional use only.

14. Background Information

Summary of Original Study Protocol in Pre-Submission

Achieving hemostasis after vascular procedures performed from the femoral artery approach is a vital component in the ultimate success of the procedure. Vascular complications are rare, but impart a significant amount of morbidity and mortality to the patient when they occur. The current “Gold Standard” is manual compression, which involves external pressure applied to the femoral artery cranial to the access site, with visual confirmation of hemostasis. Most current protocols demand 15-30 minutes of firm pressure be applied during this portion of the procedure to achieve hemostasis, followed by up to 6hours lying flat on a hard surface before ambulation. This can be very uncomfortable to the patient, and is difficult to maintain for the individual tasked with holding pressure. There is significant variability between patients with relation to body habitus and overall size. There is also variability in the skill and experience of the technician holding pressure.

About half of the procedures are closed using a variety of vascular closure devices (VCD). VCDs leave something behind in the patient, but are quick to deploy, reducing the time to achieve hemostasis. There is considerable skill required to place VCDs successfully. As a result, different types of VCD appeal to different physicians. The skilled doctor uses the VCD that the physician determines is best for his/her patient.

The SiteSeal™ device is not a VCD; it is an adjunctive compression device.

The SiteSeal™ device is placed in the catheterization laboratory, using three separate steps to improve hemostasis and remove closure process variability while leaving nothing behind. A Z-stitch is used to secure adjacent non-involved tissue and involute it over the arteriotomy site, while BioSeal powder is used to seal the wound tract itself. Compression is applied and maintained via the Adjunctive Compression Device that is sutured in place after being aligned with the sheath itself, ensuring proper positioning, and eliminating variability in pressure. The operating physician deploys the device in a minimal amount of time.

Time to hemostasis (TTH) varies with manual compression based on many variables. TTH with VCDs is really the time to deploy the device since hemostasis is achieved as soon as deployment is complete. TTH is the time to form an immature clot; TTA is the time to form a mature clot. TTA is also economically relevant as a bed is freed up only after ambulation and not after hemostasis. This trial compares an adjunctive hemostasis device to a VCD. The relevant effectiveness measure is TTA.

We postulate that the Wound Care 360° SiteSeal™ Adjunctive Compression Device is not inferior to Perclose VCD for safety during placement, time to hemostasis, time to ambulation, deployment safety, time to discharge, patient comfort and vascular complications associated with catheterization procedures performed via femoral artery access. The results of the trial are to quantify the safety and efficacy of the device and not to draw comparisons with other closure strategies. The primary outcome is to assess the risk for common femoral nerve damage and common femoral artery laceration.

The proposed Indication For Use is:

"The SiteSeal™ System is indicated for use in the compression of the femoral artery or vein after vessel cannulation."

15. OBJECTIVE

Primary: The primary endpoints assess the risk for common femoral nerve damage and common femoral artery laceration from the blind placement of a Z-stitch in the soft tissue above the femoral bundle.

Secondary: The secondary endpoints are to measure patient discomfort (per 24-hour phone interview), and the 30-day incidence of major and 30-day incidence of minor complications (per patient follow-up visit).

Patient Discomfort:

- a. Patient discomfort @ discharge from the catheterization lab:
- b. Patient discomfort @ 24 hours after the procedure:

30day Major Complications:

- a. Vascular repair or the need for vascular repair (via surgery, ultrasound guided compression, transcatheter embolization, or stent graft)
- b. Access site related bleeding requiring transfusion
- c. Any new ipsilateral lower extremity ischemia documented by patient symptoms, physical exam, and/or decreased or absent blood flow on lower extremity angiogram
- d. Surgery or the need for surgery for access site related nerve injury
- e. Permanent (lasting >30 days) access site related nerve injury
- f. Access site related infection requiring intravenous antibiotics and/or extended

hospitalization

30Day Minor Complications:

- a. Non treated pseudoaneurysm documented by ultrasound
- b. Non treated arteriovenous (AV) fistula documented by ultrasound
- c. Pseudoaneurysm treated with ultrasound guided thrombin injection or ultrasound guided fibrin adhesive injection
- d. Access site hematoma greater than or equal to 6 cm
- e. Access site related bleeding requiring greater than 30minutes to achieve hemostasis
- f. Late (following hospital discharge) access site related bleeding
- g. Ipsilateral lower extremity arterial emboli
- h. Transient loss of ipsilateral lower extremity pulse
- i. Ipsilateral deep vein thrombosis
- j. Access site related vessel laceration
- k. Transient access site related nerve injury
- l. Access site wound dehiscence
- m. Localized access site infection treated with intramuscular or oral antibiotics

16. PATIENT POPULATION

This study will be performed on "all comers" requiring interventional femoral artery procedures who meet the inclusion and exclusion criteria.

Inclusion Criteria

1. Patients between the ages 19 to 90
2. Patient or his/her legally authorized representative, has given written informed consent for participation prior to the procedure
3. Procedure is an interventional procedure
4. Patient is willing to undergo all study procedures and adhere to data collection and follow-up requirements
5. Patient is a candidate for elective, non-emergent cardiac or peripheral vascular catheterization from the femoral artery approach
6. Patient is willing to have a pre/post procedure ultrasound.

Exclusion Criteria

1. Patients are <19 years old
2. Patients are >90 years old
3. Patient has received Glycoprotein (GP) IIb/IIIa inhibitors
4. Patient or patient's representative is unable to provide written informed consent.

5. Patient is unable or unwilling to adhere to data collection and follow-up requirements
6. Procedure is emergency Percutaneous Coronary Intervention (PCI)
7. Patient is on dialysis
8. Patient has a known diagnosis of fibromyalgia
9. Patients with acute coronary syndrome (i.e., unstable angina or myocardial infarction) ≤ 48 hours before this catheterization procedure.
10. Patients with systolic blood pressure < 90 mm Hg at the end of the catheterization procedure
11. Patients who are immunocompromised
12. Patients with preexisting systemic infection or local infections at the access site
13. Patients who are known or suspected to be pregnant, or are lactating
14. Patients who have undergone prior or recent use of an intra-aortic balloon pump through the arterial access site above the inguinal ligament
15. Patients who have undergone prior vascular closure device use in the ipsilateral common femoral artery ≤ 30 days before this catheterization procedure
16. Patients who have undergone prior use of manual or mechanical compression for closure in the ipsilateral common femoral artery ≤ 30 days before the catheterization procedure
17. Patients requiring a repuncture at a site previously punctured within 48 hours of the catheterization procedure
18. Patients who have undergone an antegrade puncture
19. Patients with puncture sites believed to be in the profunda femoris artery, superficial femoral artery, or at the bifurcation of these arteries
20. Patients with puncture tract angle >55°
21. Patients who are suspected to have experienced a femoral artery back wall puncture or who underwent > 1 femoral artery puncture during the catheterization procedure
22. Patient with significant anemia (hemoglobin < 10 g/dL, Hct < 30%)
23. Patients with a known bleeding disorder, including thrombocytopenia (platelet count < 100,000 cells/µL), thrombasthenia, hemophilia, or von Willebrand's disease
24. Patients with systolic blood pressure > 180 mm Hg or diastolic blood pressure > 110 mm Hg at the end of this catheterization procedure, unless systolic and/or diastolic pressure was lowered by pharmacological agents prior to the end of the catheterization procedure

25. Patients with a baseline International Normalized Ratio (INR) >1.5 (e.g., on warfarin therapy)
26. Patients whose Activated Clotting Time (ACT) >300seconds at the end of the catheterization procedure
27. Patients who have undergone administration of low molecular weight heparin (LMWH) within 8hours of this catheterization procedure
28. Patients in whom continued heparin or other anticoagulant/antiplatelet therapy is planned for this patient (with the exception of glycoprotein IIb/IIIa inhibitor therapy) during the first few hours following the catheterization procedure
29. Patients having a complication or complications at the femoral artery access site during the catheterization procedure including bleeding, hematoma, intraluminal thrombus, pseudoaneurysm, or arteriovenous fistula
30. Patients with an ipsilateral or bilateral lower extremity amputation(s)
31. Patient known to require extended hospitalization (e.g., patient is undergoing cardiac surgery)
32. Patients who have a planned endovascular procedure within the next 30days after the catheterization procedure
33. Patients who are currently participating in another investigational study that has not concluded the follow-up period
34. Patients who have already participated in the Investigational Device Exemption (IDE) study
35. Patients who cannot adhere to or complete the study for any reason including but not limited to geographical residence or life-threatening disease

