18. METHODS / STUDY DESIGN

Institutional Review Board (IRB) approval will first be obtained. A subject's participation is a one-time event (plus follow-up) that occurs after obtaining informed consent. The subjects will not incur any costs associated with the study procedures.

At the catheter lab site, subjects will be screened through a standard of care history. After determining that the patient qualifies for enrollment into the study, an investigator or delegated study personnel will obtain an informed consent. After the patient's informed consent is obtained, study personnel will interview the subject and document subject data, including their age, gender, race, and patient history into their file. The subject source data is then recorded on a sponsor-provided Case Report Form (CRF).

Each subject will undergo the doctor-determined interventional procedure before closing with SiteSeal™.

The first 50 patients will receive a pre-device deployment ultrasound of the access site on the day of catheterization and a post-procedure ultrasound (after device removal and no later than the 30day follow-up) to detect silent complications, including vascular injury requiring repair, pseudoaneurysms requiring thrombin or fibrin adhesive injections, or bleeding requiring transfusions.

All patients will return for a follow-up visit at 30 days (± 1 week) post-procedure. A physician investigator (i.e. principal investigator, sub-investigators, physician assistants and/or nurse practitioners associated with the investigators) will examine the femoral artery access site. Any access site-related complications will be reported to the PI.

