19. ANALYSIS OF RESULTS

For each patient, a separate set of Case Report Forms (CRFs) will be completed and comprise the following information:

- Inclusion/exclusion criteria
- Demographics: Age in years, Sex, Race, Height, Weight, BMI.
- Procedure-Related Data
- Medication history
- Previous diagnostic and/or interventional endovascular procedures
- Catheterization procedure data

Primary Endpoints

- Risk for common femoral nerve puncture and common femoral artery laceration (or needle penetration) from blind placement of the Z-stitch.
 - Nerve puncture risk is defined as "the incidence of an involuntary leg muscle contraction and an auditory response at the time of placing the device".

- Common femoral artery laceration (or needle penetration) is defined as "a common femoral artery laceration (or needle penetration) with resultant bleeding or hematoma > 6 cm diameter".

Secondary Endpoints

- Patient Discomfort @ discharge from the catheterization lab and @ 24 hours' post procedure (per phone interview)
 - a. 1-10 scale with 10 being intense pain
- Assessment of complications (major and minor) 30days after leaving the catheterization lab (per visit to physician investigator).

Major complications:

- b. Vascular repair or the need for vascular repair (via surgery, ultrasound-guided compression, trans-catheter embolization, or stent-graft)
- c. Access site-related bleeding requiring transfusion
- d. Any new ipsilateral lower extremity ischemia documented by patient symptoms, physical exam, and/or decreased or absent blood flow on lower extremity angiogram
- e. Surgery or the need for surgery for access site-related nerve injury
- f. Permanent (lasting > 30 days) access site-related nerve injury
- g. Access site-related infection requiring intravenous antibiotics and/or extended hospitalization

Minor Complications

- a. Non-treated pseudoaneurysm documented by ultrasound
- b. Non-treated arteriovenous (AV) fistula documented by ultrasound
- c. Pseudoaneurysm treated with ultrasound-guided thrombin injection or ultrasound-guided fibrin adhesive injection
- d. Access site hematoma greater than 6cm
- e. Access site-related bleeding requiring greater than 30minutes to achieve hemostasis
- f. Late (following hospital discharge) access site-related bleeding
- g. Ipsilateral lower extremity arterial emboli
- h. Transient loss of ipsilateral/contralateral lower extremity pulse
- i. Ipsilateral deep vein thrombosis
- j. Access site-related vessel laceration

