20. SAFETY/RISKS

The study device comprises no risks that are in addition to manual compression with the exception of placing a blind suture around the arteriotomy site.

The blind suture carries a risk of damaging the common femoral nerve (CFN) or lacerating (or needle penetration of) the common femoral artery (CFA).

Several steps are taken to mitigate this risk.

1. The J195 suture uses a CP needle and needle holder with maximum possible depth of 12 mm (proximity control).
2. The nerve is posterior (beneath) and lateral to the common femoral artery. A portion of the psoas major muscle separates the common femoral nerve from the common femoral artery and thus is deeper than 12mm and too far lateral.
3. Revised IFU instructions teach lifting the obturator/sheath vertically to stretch soft tissue away from the femoral vessel and then place the needle through the elevated soft tissue on patients where the doctor assesses that the common femoral artery is too close to the skin surface.
4. The obturator remains in place inside the sheath for resistance control during the second needle penetration. The needle can penetrate the vessel wall (pinprick).
 - a. SiteSeal™ pressure upstream and downstream of the access site allows natural clotting to seal a vessel puncture by the needle. The attending doctor determines when to remove the device and ambulate the patient. The device remains deployed until the doctor determines that a mature clot has formed.
5. The Z-stitch penetration can potentially penetrate the vessel wall. Blood will flow between the 1.5Fr suture and suture track (path of least resistance) and be immediately obvious to the doctor.
6. The mitigation is to remove the suture and needle and then use manual pressure to seal the breach.
7. A new contraindication statement says: "Avoid use of SiteSeal™ Adjunctive Compression Device if the arterial access is at or above the inguinal ligament."

The CFA rises towards the skin surface after the inguinal ligament and then falls. The access site should be 2-3cm downstream of the inguinal ligament so that the CFA is falling where the Z-stitch is placed.

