26. STATISTICAL PLAN

Objective

The purpose of this study is to establish the safety of the SiteSeal™ Adjunctive Compression Device.

Study Design

The study design is a single arm with 90 enrolled patients, open-label, single center clinical trial.

Handling Missing Data

No imputation will be done for missing data.

Handling Dropouts

The numbers of patients who enter and complete the trial will be tabulated, and details concerning reasons for withdrawals will be listed.

Statistical Methods

Primary Safety Analyses

For the risk of each of the two primary safety endpoints, namely common femoral nerve puncture and common femoral artery laceration, percent of patients exhibiting the risk and its one-sided 95% upper confidence limit will be shown. We expect very low risk for the above two endpoints. In case that we observe no cases for each of the above endpoints, with 90 patients for the device group, we can claim that we are 95% confident that the risk is less than 3.3%.

Secondary Safety Analyses

For the risk of each of the major complications and minor complications, percent of patients exhibiting the risk and its two-sided 95% upper confidence interval will be shown. For the score of patient discomfort, the mean score and its 95% two-sided confidence interval will be reported.

Baseline Patient Characteristic Data

For each of quantitative baseline data such as age, height, BMI, and blood pressures, etc., the mean score and its 95% two-sided confidence interval will be reported.

For each of qualitative baseline data such as procedure type, presence or absence of peripheral vascular disease, and size of the introducer sheath, etc., its frequency distribution will be shown.

Populations for Analysis

All patients in this study are expected to receive the test device, and they will be categorized as intent-to-treat (ITT) patient population. All analyses will be conducted based on this ITT population.

The calculations will be performed using SAS® software for Windows¹, Version 9.4, Copyright (c) 2002-2012 by SAS Institute Inc., Cary, NC, USA.

References

1. SAS OnlineDoc Version Nine for the Web, SAS Institute Inc., Cary, NC, USA.
<http://support.sas.com/documentation/onlinedoc/sas9doc.html>

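### Exclusion 24 exempts drug-treated patients without stating a pressure they must reach, so as written it admits patients still above 180 systolic or 110 diastolic

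*Protocol*

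**What the plan says.** Protocol section 16, exclusion 24, has two parts. The limit excludes "Patients with systolic blood pressure > 180 mm Hg or diastolic blood pressure > 110 mm Hg at the end of this catheterization procedure". The exception lifts that exclusion "unless systolic and/or diastolic pressure was lowered by pharmacological agents prior to the end of the catheterization procedure".

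The only other blood pressure criterion is exclusion 10, a lower bound: "Patients with systolic blood pressure < 90 mm Hg at the end of the catheterization procedure". Section 18 places closure after the intervention: "Each subject will undergo the doctor-determined interventional procedure before closing with SiteSeal™". It asks for no further pressure reading before the device goes on. The SAP does not address eligibility.

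**The concern.** The limit is tested at the end of the procedure, and the window for the exception closes at the same moment. Because the exception says only that pressure was lowered, and not to what level, any drug-induced fall in either component appears to satisfy it. A patient who went from 220/105 to 195/100 would qualify while still above the systolic limit.

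The first thing at stake is patient safety. Section 20 accepts that the needle may enter the vessel wall and relies on the device to contain this: its "pressure upstream and downstream of the access site allows natural clotting to seal a vessel puncture by the needle". High arterial pressure could plausibly work against that seal, and the limits in exclusion 24 suggest the sponsor thought pressure mattered.

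Endpoints could also be touched. Section 19 defines the primary artery event as "a common femoral artery laceration (or needle penetration) with resultant bleeding or hematoma > 6 cm diameter", so whether a needle injury counts depends on bleeding or hematoma, which pressure may influence. Bleeding without a needle injury is not a primary event. Several minor complications could be affected in the same way: hematoma, late bleeding, and "Access site-related bleeding requiring greater than 30minutes to achieve hemostasis". The nerve endpoint has no stated link to pressure.

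The last issue is consistency. Section 17 plans several practitioners. If the clause has two readings, operators may enroll differently, and a monitor cannot say which choice is a protocol deviation.

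**Working it through.** **The plan's own figure.** The one statistical figure is the bound of 3.3% for 0 events in 90 patients (Protocol section 26; SAP, Primary Safety Analyses). It reproduces: the exact one-sided 95% limit is 1 − 0.05^(1/90) = 0.0327, or 3.27%, and the rule of three gives 3/90 = 3.33%. Nothing below depends on it. The check of exclusion 24 is one of logic.

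**The rule as written.** Let *above* mean that systolic is over 180 or diastolic over 110 at the end of the procedure. Let *lowered* mean that a drug reduced either component before the end. Then:

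excluded = *above* AND NOT *lowered*.

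**The four possible cases.**

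| Pressure at end | Lowered by drug | Limit alone | Literal exception | Exception read as lowered to ≤ 180 and ≤ 110 |
|---|---|---|---|---|
| Within both limits | Yes | Eligible | Eligible | Eligible |
| Within both limits | No | Eligible | Eligible | Eligible |
| Above at least one | Yes | Excluded | **Eligible** | Excluded |
| Above at least one | No | Excluded | Excluded | Excluded |

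Compared with the limit alone, the literal exception changes 1 of 4 cases, and the stricter reading changes 0 of 4. These are logical cases, not patient frequencies.

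**Check with values.** Take starting systolic pressures of 170, 190 and 210, and end pressures of 160, 180, 185 and 200, with a drug-induced fall.

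- End pressure at or below 180: five combinations (170 to 160; 190 to 160 or 180; 210 to 160 or 180). The patient is eligible with or without the exception in all five.
- End pressure above 180: three combinations (190 to 185; 210 to 185; 210 to 200). The literal wording admits all three.

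**The effect of and/or.** A fall in one component is enough. A patient whose systolic pressure is brought from 190 to 180 while diastolic stays above 110 is also admitted.

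**Does anything else close the gap?** Exclusion 10 bounds systolic pressure from below only. Section 18 has no later pressure check. Neither document states a target. By contrast, two other end-of-procedure criteria, exclusion 10 (systolic below 90) and exclusion 26 (activated clotting time above 300 seconds), are plain cut-offs with no exception.

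**The case against.** The best reply is that the intent is obvious. The sentence names two limits and then speaks of lowering, and the natural sense is lowered out of the excluded range. On that view the clause is surplus wording that reassures staff that drug-controlled pressure is acceptable. The end of the procedure also need not be a single instant: a high reading late in the case could be treated and brought down before closure, and the clause would then have a use. This is probably what was meant. But the text does not say so, and even the late-reading version needs a level to be reached, which is the missing element. A reader who assumes every clause has a purpose is led to the permissive reading.

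The other points concern weight, and most of them stand:

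- The affected group may be small. Patients must be elective, treated, partly responsive and still above a limit. The documents give no frequency.
- The link from pressure to the endpoints is clinical inference. Section 20 discusses needle depth, anatomy and access location, not blood pressure.
- If high pressure does increase bleeding, admitting these patients would raise the observed event rate and its upper limit in this single-arm study. It would not flatter the device. This answers a charge of favorable bias but not the safety concern.
- Safeguards exist: the attending doctor decides when the device comes off, a visible breach is treated by manual pressure, and the safety committee reviews adverse events. None of them sets a pressure limit.

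**Conclusion.** The concern holds. As written, the only patients whose eligibility the exception can change are those the limit was meant to keep out. Read the other way, the exception has no effect.

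The conclusion is confined to the literal reading; the intended meaning may well be lowered to 180/110 or below. It also assumes that pressure at the end of the procedure stands for pressure at placement, since closure follows and no later reading is required. The missing target is certain from the text. The clinical consequence is plausible but not quantified: the number of patients is unknown, no effect on any endpoint can be computed, and no sample size or confidence limit in the plan depends on it. The case for changing the text rests on patient protection and a criterion with one meaning for all operators.

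**What to change.** Delete the exception from exclusion 24. The limit alone already admits every patient whose pressure is controlled by the end of the procedure, with or without drugs.

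If the sponsor wants to say expressly that drug control is acceptable, reword it along these lines: *patients whose pressure was lowered by pharmacological agents to systolic ≤ 180 and diastolic ≤ 110 mm Hg by the end of the procedure are eligible.* This admits the same patients as deletion. Its value is clarity, and it replaces and/or with a requirement on both components.

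The cost is one sentence and possibly a few more screen failures. Those patients can be closed by manual compression, which section 14 describes as the current standard. The analysis does not change.
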